#### 4.6.3.2. Laboratory and Adverse Event for Hepatic Safety

Hepatic labs include

- alanine aminotransferase (ALT)
- aspartate aminotransferase (AST)
- total bilirubin (TBL)
- direct bilirubin (DBL)
- serum alkaline phosphatase (ALP), and
- gamma-glutamyltransferase (GGT).

When criteria are met for hepatic evaluations, investigators will conduct close monitoring of hepatic symptoms and liver tests, perform a comprehensive evaluation for alternative causes of abnormal liver tests, and complete follow-up hepatic safety CRFs.

The table below lists summary TFLs for the analysis of hepatic laboratory data.

Analysis	Details		
Abnormal postbaseline categories – hepatic safety parameters	ALT: The number and percentage of participants with a measurement greater than or equal to 1 time (1X), 3 times (3X), 5 times (5X), 10 times (10X), and 20 times (20X) the performing laboratory ULN during the postbaseline period will be summarized for all participants with a postbaseline value.		
	AST: The number and percentage of participants with a measurement greater than or equal to 1 time (1X), 3 times (3X), 5 times (5X), 10 times (10X), and 20 times (20X) the performing laboratory ULN during the postbaseline period will be summarized for all participants with a postbaseline value.		
	ALP: The number and percentage of participants with a measurement greater than or equal to 2 times (2X) and 3 times (3X) the performing laboratory ULN during the postbaseline period will be summarized for all participants with a postbaseline value.		
	TBL: The number and percentage of participants with a measurement greater than or equal to 2 times (2X), 5 times (5X), and 8 times (8X) the performing laboratory ULN during the postbaseline period will be summarized for all participants with a postbaseline value.		
	DBL: The number and percentage of participants with a measurement greater than or equal to 2 times (2X) and 5 times (5X) the performing laboratory ULN during the postbaseline period will be summarized for all participants with a postbaseline value.		
	GGT: The number and percentage of participants with a measurement greater than or equal to 2 times (2X) the performing laboratory ULN during the postbaseline period will be summarized for all participants with a postbaseline value.		
Treatment-emergent potentially drug-related hepatic disorders	Potentially drug-related hepatic disorders are defined using a custom query based on the following SMQs:  • Broad and narrow terms in the Liver-related investigations, signs and symptoms SMQ (20000008)  • Broad and narrow terms in the Cholestasis and jaundice of hepatic origin SMQ (20000009)  • Broad and narrow terms in the Hepatitis non-infections SMQ (20000010)  • Broad and narrow terms in the Hepatic failure, fibrosis and cirrhosis and other liver damage SMQ (20000013)  • Narrow terms in the Liver-related coagulation and bleeding disturbances SMQ (20000015)  These SMQs are a subset of the sub-SMQs comprising the full Hepatic Disorders SMQ. Only the sub-SMQs considered applicable to capturing potentially drug-related hepatic disorders		
	are included.  The percentage of study participants with at least one of any of the MedDRA preferred terms from any of the above SMQs will be summarized in addition to the percentages for each MedDRA preferred term.		

Analysis	Details
Hepatocellular drug-induced liver injury screening plot (TBL vs ALT or AST)	Each participant's data is plotted based on their maximum postbaseline TBL (y-axis) and transaminase (ALT or AST, whichever is higher), regardless of the time between the 2 maximum values. Lines represent TBL and transaminase cutoffs of 2X ULN and 3X ULN, respectively. A potential Hy's law case is circled and is defined as having a maximum postbaseline TBL equal to or exceeding 2X ULN within 30 days after maximum postbaseline ALT or AST equal to or exceeding 3X ULN, without cholestasis (defined as ALP less than 2X ULN).
Hepatocellular drug-induced liver injury screening table	The percentages of study participants falling in each of the 3 relevant quadrants of the plot (right upper, left upper, right lower) will be summarized in a table.
Cholestatic drug-induced liver injury screening plot (TBL vs ALP)	Each participant's data is plotted based on their maximum postbaseline TBL (y-axis) and ALP (x-axis), regardless of the time between the 2 maximum values. Lines represent TBL and ALP cutoffs of 2X ULN and 3X ULN, respectively. A potential cholestatic liver injury case is circled and is defined as having a maximum postbaseline TBL equal to or exceeding 2X ULN within 30 days after maximum postbaseline ALP equal to or exceeding 3X ULN.
Cholestatic drug-induced liver injury screening table	The percentages of study participants falling in each of the 3 relevant quadrants of the plot (right upper, left upper, right lower) will be summarized in a table.
List of Participants with potential hepatocellular drug-induced liver injury	Includes participants falling in the right upper quadrant in the Hepatocellular Drug-Induced Liver Injury Screening plot.
List of Participants with potential cholestatic drug-induced liver injury	Includes participants falling in the right upper quadrant in the Cholestatic Drug-Induced Liver Injury Screening plot.

Abbreviations: ALP = alkaline phosphatase; ALT = alanine aminotransferase; AST = aspartate aminotransferase; CRF = case report form; DBL = direct bilirubin; GGT = gamma-glutamyl transferase; MedDRA = Medical Dictionary for Regulatory Activities; SMQ = Standardized MedDRA Query; TBL = total bilirubin; ULN = upper limit of normal.

Planned and unplanned measurements will be included. The measurements do not need to be taken at the same blood draw.

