Visit Interval Tolerance (days)		±3	_	±3		±3	±3	±3	±3	±3	±3	±3	±3	±3	±3	±3	±3	±3	b Visit 6 must not occur on the same day as Visit 5.
Visit Detail			F	Т			Т	F	Т	Т	Т	F	Т	Т	Т	F	Т	F	T = telehealth visit F = fasting visit
Review SMBG 6-point profiles			X															X	Review profiles collected in preceding week. See Section 8.1.1.1.
Paper Patient-Reported Ou	itcome	es																	
Treatment-Related Impact Measure - Diabetes (TRIM-D)			X															X c	c At Visit 18 or after, if a participant changes from the autoinjector to the prefilled pen, conduct this procedure on the day the change occurs.
Diabetes Injection Device Experience Questionnaire (DID-EQ)																		Х°	changes from the autoinjector to the prefilled pen, conduct this procedure on the day the change occurs.
Electronic Patient-Reporte	d Outo	comes																	
Diabetes Treatment Satisfaction Questionnaire - Status (DTSQ-s)			X																
Diabetes Treatment Satisfaction Questionnaire - Change (DTSQ-c)																		Х°	c At Visit 18 or after, if a participant changes from the autoinjector to the prefilled pen, conduct this procedure on the day the change occurs.
Simplicity of Diabetes Treatment Questionnaire (SIM-Q)																		Х°	c At Visit 18 or after, if a participant changes from the autoinjector to the prefilled pen, conduct this procedure on the day the change occurs.

Study I8H-MC-BDCW Table 1	& L	een ead- n								Trea	itmen	t							Comments
Visit Number	1	2	3	4	5	6	7	8	9	10	11	12	13	14	15	16	17	18	
Weeks from Randomization	-3	-2	0	1	1 a	2 b	3	4	5	6	7	8	9	10	11	12	14	16	a Visit 5 occurs 3 days after Visit 4 ± 1 day.
Visit Interval Tolerance (days)		±3	_	±3		±3	±3	±3	±3	±3	±3	±3	±3	±3	±3	±3	±3	±3	b Visit 6 must not occur on the same day as Visit 5.
Visit Detail			F	Т			Т	F	Т	Т	Т	F	Т	Т	Т	F	Т	F	T = telehealth visit F = fasting visit
Basal Insulin Experience Likelihood of incorporating into routine																		Х°	changes from the autoinjector to the prefilled pen, conduct this procedure on the day the change occurs.
Laboratory Tests and Samp	ole Co	llectio	ns																
Hematology	X		X													X			
Hemoglobin A1c (HbA1c)	X		X			X		X				X				X		X	
Clinical chemistry	X		X													X			
Glucose								X				X						X	
Lipid panel			X													X			
Urinalysis	X																		
Serum pregnancy	X		X																Collect for WOCBP only.

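### The potential Hy's law circle compares the dates of two maxima, so a same-draw case goes uncircled when peak bilirubin precedes peak ALT/AST or follows it by more than 30 days

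*SAP*

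**What the plan says.** SAP Section 4.6.3.2 plots each participant's maximum postbaseline TBL against the higher of maximum ALT or AST. Position on the plot ignores timing: "regardless of the time between the 2 maximum values". Timing enters only through the circle. A circled potential Hy's law case is "defined as having a maximum postbaseline TBL equal to or exceeding 2X ULN within 30 days after maximum postbaseline ALT or AST". The transaminase threshold and the exclusion come later in that sentence: "equal to or exceeding 3X ULN, without cholestasis (defined as ALP less than 2X ULN". The section does not say which ALP value, or on what date, decides the absence of cholestasis.

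The cholestatic plot circles a case with "maximum postbaseline TBL equal to or exceeding 2X ULN within 30 days after maximum postbaseline ALP equal to or exceeding 3X ULN".

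Three further statements bear on the point:

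- The screening table works by quadrant, not by circle: "The percentages of study participants falling in each of the 3 relevant quadrants of the plot (right upper, left upper, right lower) will be summarized".
- So does the hepatocellular listing: "Includes participants falling in the right upper quadrant in the Hepatocellular Drug-Induced Liver Injury Screening plot". The cholestatic listing is built the same way.
- A note under the table says: "Planned and unplanned measurements will be included. The measurements do not need to be taken at the same blood draw".

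**The concern.** The circle is the only element of the plots, tables and listings that adds timing to quadrant position. On the hepatocellular plot it is also the only element that adds the no-cholestasis condition. It is what labels a participant a potential Hy's law case, and the value of that label lies in qualifying ALT/AST and TBL values occurring close together.

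The rule tests something else: how far apart the two highest values of the whole postbaseline period fall, and in which order. A participant can meet both thresholds at a single draw and lose the circle because a higher value of either analyte occurs at another time. The note that values need not share a draw does not help, because the dates compared are still those of the maxima.

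A reader who relies on the circle could then take an uncircled participant as having no close-in-time pair when one exists.

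**Working it through.** There is no stated figure to reproduce, because this is a derivation rule. The check codes the rule and applies it to constructed records.

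**Rule as written.** Let *lag* = (day of maximum TBL) − (day of maximum ALT/AST). Circle if maximum ALT/AST ≥3X ULN, maximum TBL ≥2X ULN, 0 ≤ lag ≤ 30 days, and ALP <2X ULN.

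**Comparison rules.**

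- Window reading: the highest TBL in days 0 to 30 after the ALT/AST peak is ≥2X ULN.
- Any-pair rule: some ALT/AST ≥3X ULN is followed on the same day or within 30 days by some TBL ≥2X ULN.

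**Assumed records.** All laboratory values are illustrative. Every record has ALT 4X and TBL 2.5X ULN at one shared draw, and ALP is taken as <2X ULN throughout. Weeks convert to days at 7 days each (Week 12 = Day 84, Week 26 = Day 182, Week 52 = Day 364, Week 57 = Day 399).

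| Record | Shared draw | Other draw that moves a peak (ALT / TBL, X ULN) | Lag (days) | As written | Window reading | Any pair |
|---|---|---|---|---|---|---|
| A | Day 84 | none | 0 | yes | yes | yes |
| B | Day 84 | Day 182: 5 / 1 | 84 − 182 = −98 | no | no | yes |
| C | Day 84 | Day 182: 1 / 3 | 182 − 84 = 98 | no | yes | yes |
| D | Day 84 | Day 87: 3.5 / 3 | 87 − 84 = 3 | yes | yes | yes |
| E | Day 84 | Day 87: 5 / 2.2 | 84 − 87 = −3 | no | yes | yes |
| E2 | Day 84 | Day 87: 5 / 1.8 | 84 − 87 = −3 | no | no | yes |
| F | Day 84 | Day 74: 5 / 1.5 | 84 − 74 = 10 | yes | yes | yes |
| G | Day 84 | Day 119: 2 / 3 | 119 − 84 = 35 | no | yes | yes |
| H | Day 364 | Day 399: 2 / 3 | 399 − 364 = 35 | no | yes | yes |
| I | Day 367 | Day 392: 2 / 3 | 392 − 367 = 25 | yes | yes | yes |

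Record I is the Week 52 and Week 57 pair with assumed window shifts of +3 and −7 days: 35 − 3 − 7 = 25.

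**Result.** The rule as written circles 4 of 10 (A, D, F, I). The window reading circles 8 of 10 and misses B and E2. The any-pair rule circles all 10. All 10 lie in the right upper quadrant.

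**Where the gaps come from.** In the protocol's Schedule of Activities, postbaseline "Clinical chemistry" is scheduled at Weeks 12, 26, 52 and 57 and at the early discontinuation visit. The nominal gaps are (26 − 12) × 7 = 98, (52 − 26) × 7 = 182 and (57 − 52) × 7 = 35 days. Protocol Section 8.2.5 adds unscheduled samples: a retest within 48 to 72 hours of a qualifying abnormality, then 1 to 3 draws a week at first if it persists or worsens. Closer sampling can keep the circle (D) or remove it (E, E2), depending on which analyte peaks first.

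**The case against.** The strongest case on the other side has three parts.

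**The circle is an annotation.** No specified table, listing or test uses it. The quadrant table counts every such participant and the listing names them, circled or not. The same SAP section also tabulates threshold exceedances for each analyte. This stands, and it sets the size of the point. A reader might infer that liver cases disappear from the report; the documents do not support that.

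**Real sampling is closer than the visit schedule.** Because every nominal gap between scheduled chemistry visits exceeds 30 days, a reader might infer that the circle can appear only when both maxima fall at one draw, or that it is lost whenever either peak falls at another visit. Neither follows. Unplanned measurements are included, the early discontinuation visit has chemistry and can fall near another visit, and the ±7-day tolerance at Visit 802 alone can bring 35 days down to 28. A TBL peak 0 to 30 days after the ALT/AST peak keeps the circle, as D, F and I show. In addition, Protocol Section 7.1.1 calls for interrupting or discontinuing study intervention at ALT or AST >3X with TBL >2X ULN, so a higher ALT peak months later (B) is possible but not the expected course. This part also stands.

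**The wording can be read another way.** The sentence could mean the highest TBL inside the 30 days after the ALT/AST peak. That is less natural, because the same table cell uses the two maxima for the plot axes, where they are clearly whole-period values. It rescues C, E, G and H. It does not rescue B or E2, where ALT peaks after the shared draw and TBL is then below 2X ULN.

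A TBL peak shortly before the ALT/AST peak is not by itself a missed case. If no qualifying TBL falls on or within 30 days after a qualifying ALT/AST draw, the any-pair rule leaves it uncircled too.

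**Conclusion.** The point holds in a narrow form and is minor. A participant with ALT/AST ≥3X ULN and TBL ≥2X ULN at the same draw loses the circle when the maximum TBL precedes the maximum ALT/AST or follows it by more than 30 days. The cholestatic flag has the same maximum-to-maximum construction, with ALP in place of ALT/AST.

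The consequence is limited to a circled set that could be incomplete. No endpoint, quadrant percentage or listing changes. How often this would happen cannot be worked out from the documents.

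The conclusion rests on the plain reading of the maxima as whole-period values. Under the window reading fewer cases are lost, but the weakness remains.

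**What to change.** Keep the plot axes, quadrant tables and listings as they are. Redefine the circles in SAP Section 4.6.3.2:

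- **Hepatocellular:** any postbaseline TBL ≥2X ULN on the same day as, or within 30 days after, any postbaseline ALT or AST ≥3X ULN, with ALP <2X ULN evaluated at a stated time tied to that pair, for example the qualifying ALT/AST draw.
- **Cholestatic:** any postbaseline TBL ≥2X ULN on the same day as, or within 30 days after, any postbaseline ALP ≥3X ULN.

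This keeps the SAP's thresholds, its 30-day limit and its direction in time. The cost is the SAP wording and the matching derivation condition for each flag. No new data are needed.

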#### 4.6.3.3. Clinical Laboratory Evaluations

For the following selected laboratory measures:

- Liver enzyme tests: ALT, ALP, AST, GGT, DBL and Total Bilirubin
- Lipid measures: Triglycerides, total cholesterol, LDL-C, and HDL-C (results from fasting samples)

MMRM model (as described in Section 4.6) will be used for the observed values, change from baseline and percentage change from baseline, for which log-transformation will be applied.

Geometric LS means will be provided. Analyses will be provided in both international units (SI) and conventional units (CN) if they are different.

Box plots with descriptive statistics for the observed values and change from baseline will be provided by treatment group and visit.

For other laboratory measures, descriptive summaries will be provided for the observed values and change from baseline by treatment group and visit.

The percentages of patients with elevated or low values meeting specified levels (see Appendix 10, Section 6.10 at any time postbaseline (including scheduled and unscheduled measurements) will be summarized and compared between treatment groups using risk difference and 95% confidence interval.

A listing of abnormal laboratory analytes collected quantitatively (high or low during postbaseline using Level 2 definitions in Appendix 10, Section 6.10) and qualitatively (abnormal during postbaseline) will be provided, including participant identification, treatment group, laboratory sample collection day (that is, days from start of study drug), analyte name, abnormal result, reference low or high limits, and level 2 cut-off value if applicable.

Scatter plots of maximum-by-maximum measurements and minimum-by-minimum measurements will not be created a-priori. They may be created if warranted after review of the planned tables and figures, using Figures 6.3 and 6.4 from the Analysis and Displays for Labs white paper (PHUSE 2022) as the model. Analysis Data Model (ADaM) datasets will include variables to enable the creation of scatter plots for use in either an interactive tool or for ad-hoc figures.

#### Scatter plots to support vital sign evaluations

Scatter plots of maximum-by-maximum measurements and minimum-by-minimum measurements will not be created a-priori. They may be created if warranted after review of the planned tables and figures, using Figures 6.3 and 6.4 from the Analysis and Displays for Labs white paper (PHUSE 2022) as the model. ADaM datasets will include variables to enable the creation of scatter plots for use in either an interactive tool or for ad-hoc figures

### **4.6.4.** Device Product Complaints

A summary of all product complaints, inclusive of device product complaints that lead to an AE and/or SAE will be included by category. Additional summaries may be provided as deemed appropriate.

## 4.7. Other Analyses

### 4.7.1. Immunogenicity

A participant is evaluable for TE-ADA if the participant has a nonmissing baseline ADA result, and at least 1 nonmissing postbaseline ADA result.

A participant who is evaluable for TE-ADA is TE-ADA+ if either of the following holds:

- Treatment-induced ADA: the participant has baseline status of ADA Not Present and at least 1 postbaseline status of ADA Present with titer ≥ 1:40, which is 2 × MRD of the ADA assay (MRD=1:20).
- Treatment-boosted ADA: the participant has baseline status of ADA Present and at least 1 postbaseline status of ADA Present with the titer being ≥2 dilutions (4-fold) of the baseline titer. That is, the participant has baseline (B) status of ADA Present, with titer 1:B, and at least 1 postbaseline (P) status of ADA Present, with titer 1:P and P/B≥4.

Refer to PSAP for all definitions and additional details for immunogenicity.

All analyses will be based on all evaluable TE-ADA participants. The baseline ADA status will be summarized by treatment group. The number and percentage of participants who are TE-ADA+ will be summarized by treatment group. The summary will include the number and percentage of participants with treatment-induced ADA and treatment boosted ADA. A summary

of titer values will be provided for participants who are TE ADA positive. This analysis will be performed for the following periods:

- The treatment period up to treatment discontinuation
- The entire postbaseline period, including safety follow-up

A number of additional analyses of the immunogenicity data from this study will be presented in an integrated summary document, alongside data from other studies. The analyses to be performed are described in the PSAP.

#### 4.7.2. Subgroup Analyses

The interaction effects will be evaluated using a significance level of 0.05, unadjusted. Separate analysis without the terms related with the subgroup will be performed for each subpopulation. Subgroup analyses will be conducted as defined in this section. Additional subgroup analysis may also be performed as appropriate.

## 4.7.2.1. Subgroup Analyses in HbA1c

Subgroup analyses in HbA1c and change in HbA1c from baseline to Week 52 will be conducted with subgroups defined as:

- Age (<65 years and  $\ge65$  years)
- Baseline HbA1c stratum (<8.0% and  $\ge8.0\%$ )
- Ethnicity
- Gender
- Race (White, American Indian or Alaska Native, Asian, and Black or African American)
   Native Hawaiian or Other Pacific Islander, and Multiracial are not included in the subgroup analysis because the number of subjects is too small.
- Region (US and non-US)
- Region (North America and South America)
- GLP-1 RA use at randomization
- Estimated Glomerular Filtration Rate (eGFR) at baseline ( $<60, 60 <90, and <math>\ge 90$  mL/min/1.73 m^2)
- Duration of diabetes (< median and  $\ge$  median)
- Insulin Dose (>400 U at anytime and <= 400 U at anytime), where
  - o ">400 U at anytime" group includes participants receiving insulin glargine with weekly dose >400 U at anytime up to week 52 (Visit 33) or participants who switch to prefilled pen for LY3209590, and
  - "<= 400 U at anytime" group includes participants receiving insulin glargine with weekly dose <=400 U at anytime up to Week 52 (Visit 33) or participants receiving LY3209590 with auto injector for the whole treatment period.

Analyses for HbA1c and its change will be performed within each subgroup using the same MMRM model for efficacy estimand described for the primary analysis in Section 4.3.2. In addition, the interaction effects will be assessed using the model including the same fixed effects and covariate given for the primary analysis model plus factors of subgroup, 2-way interaction of

subgroup and treatment, 2-way interaction of subgroup and visit, and 3-way interaction of treatment, visit and the subgroup.

Another subgroup analysis for HbA1c will be conducted for treatment regimen estimand. The ANCOVA analysis for HbA1c for the treatment regimen estimand as described in Section 4.3.2. will be performed within each subgroup. The statistical inference will be based on the multiple imputation framework by Rubin (1987). The p-value for treatment by subgroup interaction will be calculated using a chi-square test based on estimated treatment differences within each subgroup. (See details in Appendix 11 [Section 6.11]).

## 4.7.2.2. Subgroup Analyses in Hypoglycemia

Subgroup analyses in documented Level 2/3 hypoglycemia, non-nocturnal, and nocturnal hypoglycemia rates during 0 to 52 weeks will be conducted with subgroups defined as:

- Baseline HbA1c stratum (<8.0% and  $\ge8.0\%$ )
- Region (North America and South America)
- Region (US and non-US)
- GLP-1 RA use at randomization
- eGFR at baseline ( $<60, 60 <90, \text{ and } \ge 90 \text{ mL/min/}1.73 \text{ m}^2$ )

The hypoglycemia rates will be analyzed using a negative binomial regression including the same independent variables for hypoglycemia event analyses (see Section 4.6.3.1) plus factors of subgroup, 2-way interaction of subgroup and treatment. Separate analysis without the terms related with the subgroup will be performed for each subpopulation.

